#### 7.13.1 Adverse Events

Adverse events will be recorded using MedDRA v23.1 or a more up-to-date version by the time of database lock. A treatment emergent adverse event (TEAE) is defined as:

- Any AE that has an onset on or after the first dose of SP-102 or placebo
- Any pre-existing AE that has worsened in severity on or after the first dose of SP-102 or placebo.

A treatment-related TEAE is any study medication related TEAE and/or study procedure related TEAE.

A study medication treatment-related AE is defined as one of the following; possibly related, probably related, or definitely related to the study drug. If an AE has a missing relationship to study medication it is assumed to be related to the study drug for analysis purposes.

A study procedure treatment-related AE is defined as an AE related to the study procedure.

The intensity/standard toxicity grade of an AE is defined as an AE being Grade 1 (Mild), Grade 2 (Moderate), Grade 3 (Severe), or Grade 4 (Life-Threatening).

Severe intensity (Grade 3) will be assumed for an AE with missing intensity.

The summary of TEAEs will include the total number and percentage of subjects reporting an event. In counting the number of events reported, a continuous event, i.e. reported more than once and which did not cease, will be counted only once; non-continuous AEs reported several times by the same subject will be counted as multiple events.

TEAEs will be assigned to one of the two treatments (SP-102 or Placebo). AEs starting while on Placebo but before the repeat injection will be assigned to Placebo. AEs starting on or after the repeat injection of SP-102 will be assigned to SP-102. Any pre-existing TEAE that started during the Placebo use and that has worsened in severity on or after the repeat injection of SP-102 will be assigned to SP-102.

Any TEAEs will be summarized by treatment, for each post-randomization treatment period:

- Entire treatment period
- Occurring after the randomization injection, but prior to a second injection (of SP-102)
- Occurring after the second injection (of SP-102)

The following incidence (number and percent of subjects reporting the AE at least once during the study) of TEAEs tables will be presented:

- Overall incidence and the number of TEAEs, related TEAEs, serious adverse events (SAEs), related SAEs, TEAEs leading to withdrawal, and TEAEs leading to death.
- TEAE by system organ class and preferred term, incidence and number of events
- Study medication-related TEAE by system organ class and preferred term, incidence and number of events
- Study procedure-related TEAE by system organ class and preferred term, incidence and number of events
- Serious TEAE by system organ class and preferred term, incidence and number of events
- Serious study medication-related TEAE by system organ class and preferred term, incidence and number of events
- Serious study procedure-related TEAE by system organ class and preferred term, incidence and number of events
- TEAE by system organ class, preferred term and intensity, incidence
- Serious TEAE by system organ class, preferred term and intensity, incidence
- Treatment-related TEAE by system organ class, preferred term and intensity, incidence

- TEAEs leading to early termination of the study by system organ class and preferred term, incidence
- Listing of Serious TEAEs (presented in the Table section of the appendices)
- Listing of Deaths (presented in the Table section of the appendices)

Additionally, an overall summary of the incidence and the number of TEAEs, related TEAEs, SAEs, related SAEs, TEAEs leading to withdrawal, and TEAEs leading to death through 12 weeks, and a summary of incidence and number of events of TEAEs by system organ class and preferred term through 12 weeks will be presented as follows:

- by four groups (SP-102/SP-102, PBO/SP-102, SP-102/none, and PBO/none)
- by treatment (Placebo, SP-102) but only for the subjects in the PBO/SP-102 group
- by exposure to SP-102, that is, Exposed vs. Not Exposed to SP-102; the Exposed group will include the subjects that have received SP-102 for the index injection and/or have a repeat injection while Non-Exposed group will include the subjects that have received Placebo for the index injection and do not have repeat injection

All AEs will be listed.

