4.1.5 Assessing Intensity and Relationship

All AEs will be assessed on 2 descriptive parameters: intensity and relationship to the IP:

- Intensity refers to the severity of an event and references impact on a subject's functioning.
- Relationship refers to the likelihood that the event being assessed was caused by the IP.

Intensity

Each AE will be classified according to [Appendix N](#).

When changes in the intensity of an AE occur more frequently than once a day, the maximum intensity for the experience should be noted. If the intensity category changes over a number of days, those changes should be recorded separately (with distinct onset dates).

Relationship

Each AE will be assessed as to its relationship to the IP, based on the following criteria. Although the attribution by the investigator will be collected for reported events, for analytic purposes a temporal association with the use of the IP will be assumed sufficient for at least plausible association.

Investigators are required to assess the causal relationship (ie, whether there is reasonable possibility that the study drug caused the event) using the following definitions:

- Unrelated: A clinical event, including laboratory test abnormality, with a temporal relationship to study drug administration that makes a causal relationship improbable, and/or in which other drugs, chemicals or underlying disease provide plausible explanations of the event.
- Possibly Related: A clinical event, including laboratory test abnormality, with a reasonable time sequence to administration of the study drug, but that could also be explained by concurrent disease or other drugs or chemicals. Information on study drug causality may be lacking or unclear.
- Probably Related: A clinical event, including laboratory test abnormality, with a reasonable time sequence to administration of the study drug, unlikely to be attributed to concurrent disease or other drugs or chemicals, and that follows a clinically reasonable response on re- administration (rechallenge) or withdrawal (dechallenge) of the study drug.
- Definitely Related: A clinical event, including laboratory test abnormality, with a temporal relationship to study drug administration that makes a causal relationship definite and is clearly related to use of the IP.

When assessing the relationship to the IP, the following criteria will be considered:

- Positive rechallenge

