5.2.9.1 Adverse Events

All AEs will be coded using the most current version of MedDRA.

The incidence of treatment-emergent AEs (TEAEs) (number and percent of subjects reporting the AE at least once during the study), SAEs, AEs related to study treatment, SAEs related to treatment, and AEs leading to study discontinuation will be summarized by treatment.

A TEAE is defined as any AE that has an onset on or after the dose of IP, or any pre-existing condition that has worsened on or after the first dose of IP.

The incidence of TEAEs and treatment-related AEs will also be summarized by maximum severity and most-related relationship to IP by MedDRA primary system organ class and preferred term. The summary will include the total number and percentage of subjects reporting an event. In counting the number of events reported, a continuous event, ie, reported more than once and which did not cease, will be counted only once; non-continuous AEs reported several times by the same subject will be counted as multiple events.

Any TEAEs will be summarized by treatment group, for each post-randomization treatment period:

- Occurring after the randomization injection, but prior to a second injection (of SP-102)
- Occurring after the second injection (of SP-102)

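### SAP 7.13.1 assigns adverse events by start date but does not link the separately dated intensity entries that the protocol creates, so a placebo-period event that improves after the repeat injection can also be counted under SP-102

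*SAP*

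**What the plan says.** **Recording (Protocol 4.1.5).** Two rules govern intensity changes. For rapid changes: "When changes in the intensity of an AE occur more frequently than once a day, the maximum intensity for the experience should be noted". For slower ones: "If the intensity category changes over a number of days, those changes should be recorded separately (with distinct onset dates". The second rule does not separate improvement from worsening.

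**Assignment (SAP 7.13.1).** Each treatment-emergent AE (TEAE) is to go to one of two treatments, by three sentences:
- The first covers a placebo subject's events up to the repeat: "AEs starting while on Placebo but before the repeat injection will be assigned to Placebo".
- The second covers everything that begins later, and again works by start date: "AEs starting on or after the repeat injection of SP-102 will be assigned to SP-102".
- The third covers a placebo-period event that "has worsened in severity on or after the repeat injection of SP-102 will be assigned to SP-102".

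**Counting (SAP 7.13.1, and the same rule in Protocol 5.2.9.1).** For the number of events, "a continuous event, i.e. reported more than once and which did not cease, will be counted only once".

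**Outputs.** SAP 7.13.1 summarises TEAEs by period, including one that begins at the second injection. It also plans a Placebo versus SP-102 split through 12 weeks within the PBO/SP-102 group. The tables report subjects (number and percentage), and many also report numbers of events.

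**The concern.** The protocol turns one continuing AE into several dated entries, while the SAP's assignment sentences read as if each AE had a single start. For worsening the two roughly agree, because the worsened entry has a later date and the SAP wants it under SP-102. For improvement they conflict: the milder entry also has a date after the repeat, and the start-date sentence, applied to it literally, sends it to SP-102.

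The error runs one way. Resolving placebo-period events are added to SP-102 and to the post-repeat period, and none are taken away, so apparent harm after the repeat injection is overstated. Evaluating the safety of single and repeat injection is a stated secondary objective. Two competent programmers could also produce different tables from the same data.

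**Working it through.** The plan states no figure to reproduce on this point, so the check sets the rules side by side and traces cases through them.

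**Inputs.** The recording rules are in Protocol 4.1.5, and the assignment and counting rules in SAP 7.13.1. Protocol section 4 follows AEs until they resolve or stabilise, and the repeat may be given from Week 4. An AE that began on placebo can therefore still be open at the repeat.

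**Cases.** A placebo-group subject has a Grade 2 AE that is ongoing at the repeat injection and never ceases.

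| Course after the repeat | Entries under Protocol 4.1.5 | Rules applied to each entry | Entries linked, first onset governs |
|---|---|---|---|
| Unchanged | one, dated before the repeat | Placebo | Placebo |
| Falls to Grade 1 some days later | two, the second dated after the repeat | Placebo **and** SP-102 | Placebo only |
| Rises to Grade 3 some days later | two, the second dated after the repeat | Placebo and SP-102 | SP-102, by the worsening sentence |

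The second row is the problem. The first entry stays where it was and a second attribution is added, so one event puts the subject in both columns.

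**Which reading the SAP supports.** The linked one.
1. The worsening sentence covers "Any pre-existing TEAE that started during the Placebo use and that has worsened in severity on or after the repeat injection of SP-102". If each entry were already placed by its own onset date, that sentence would do almost no work, since the worsened entry would already start after the repeat.
2. The counting rule recognises AEs reported more than once without ceasing, which presupposes that entries are joined.
3. Placing one event in both columns conflicts with giving each TEAE one treatment.

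**Why the text does not settle it.** The counting sentence is limited to the number of events. It does not say which onset fixes treatment or period, which column keeps the single event, or how subject incidence is formed. The worsening sentence says nothing about improvement. Both sections are legible in the public documents, and neither contains a linking rule.

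**Which tables can change.**
- Placebo versus SP-102 split in PBO/SP-102 subjects: yes.
- After-second-injection summary: yes. SP-102/SP-102 subjects can enter it through a step-down entry, but their treatment is SP-102 either way.
- Overall incidence by the four groups, or by Exposed versus Not Exposed: no. Membership depends on the injections received, and the subject already counts there through the first entry.

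**Illustration only.** The documents give no AE frequency and no repeat-injection rate, so every input here is assumed. Take 100 PBO/SP-102 subjects, 10 with a genuinely new AE after the repeat, and 2, 5 or 10 others whose only post-repeat entry is a step-down.
- Linked: 10/100 = 10%.
- Entry by entry: (10 + 2)/100 = 12%, (10 + 5)/100 = 15%, or (10 + 10)/100 = 20%.

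This shows direction and mechanism. It is not an estimate.

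**The case against.** The best defence is that the SAP, read as a whole, already works at the level of the AE. The worsening sentence and the counting rule make sense only on that footing, and the protocol speaks of changes in the intensity of an AE, not of new AEs. The case report form layout is not in the documents and may link entries to a parent event. The tables are descriptive, any error goes against the active drug, and all AEs are listed, so a misplaced entry could be traced.

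Most of this stands as evidence of intent. It does not supply the missing rule: the stated assignment variable is the start date, and the recorded data carry several start dates for one AE.

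A reader might infer stronger points that the documents do not support:
- *Every intensity change produces a new entry.* It does not. Where intensity changes more often than once a day, only the maximum is noted.
- *The placebo event is transferred to SP-102.* It is not. The first entry remains under Placebo, so the fault is double attribution.
- *The main AE comparison is distorted.* The safety endpoint in Protocol 5.2.9 compares four groups defined by injections received, and their overall incidence cannot move.

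**Conclusion.** The point holds as an unreconciled mismatch between how the protocol records AEs and how the SAP assigns them. Taken literally, the two rules count an improving placebo-period AE a second time, under SP-102 and after the second injection, against the SAP's own evident intent. The reach is the two descriptive outputs identified above; efficacy and type I error are unaffected.

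The conclusion rests on two assumptions: that sites follow Protocol 4.1.5 and enter multi-day improvements separately, and that no linking rule exists outside the visible text. The size cannot be estimated from the documents. It depends on how many PBO/SP-102 subjects have an AE open at the repeat that later drops a grade and have no other post-repeat TEAE. For the period summary, SP-102/SP-102 subjects in the same position also matter.

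**What to change.** Add to SAP 7.13.1:
1. Consecutive entries of the same AE term in one subject, with no intervening cessation, are linked into one event.
2. The first onset of the linked event determines its treatment and its period.
3. A linked event that began before the repeat injection is assigned to SP-102 and to the post-repeat period only if a later entry's grade exceeds the last grade recorded before the repeat. An improved or unchanged event keeps its original assignment.
4. The same linked events are used for subject incidence and for numbers of events.

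For SP-102/SP-102 subjects, only the period part of these rules has any effect.

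The cost is a short SAP clarification and one derivation that links consecutive same-term entries. No new data are needed.

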Each subject will have the option of receiving 1 supplemental OL TF injection of SP-102 ("repeat injection"). To qualify for the repeat injection, subjects must meet Repeat Injection Inclusion Criteria, NPRS pain score in the affected leg, and investigator judgment, which includes a safety evaluation demonstrating no signs or symptoms of adrenal suppression or other safety concerns. The repeat injection may be administered between Weeks (W) 4 and 20. Eligible subjects will receive OL SP-102 repeat injection regardless of their initial treatment assignment (SP-102 or placebo).

In case of inadequate control of radicular pain, up to [REDACTED] will be allowed per day. The subject should be instructed to avoid use of acetaminophen within 6 hours prior to recording an NPRS score. Doses of rescue medication and time taken will be collected in the eDiaries until W12 and thereafter as a concomitant medication.

The subject will complete the eDiary twice daily approximately 12 hours apart (± 2 hours) to record their NPRS scores for pain in the previous 12 hours for 12 weeks following index injection. Thereafter, NPRS scores will be recorded at clinic visits.

All subjects will be seen at the clinic on D15, and every 4 weeks (ie, W4 [D29], W8 [D57], W12 [D85], W16 [D113], W20 [D141], and W24 [D169]) after the DB index injection for up to 24 weeks. Subjects receiving the OL repeat SP-102 injection will also be seen at the clinic 14 days after the repeat injection and continue the DB planned visits as well. The subject will also be contacted by telephone by the site staff 2 days after each IP injection to discuss their progress, any medications they are taking, and if they have had any adverse events (AEs).

The study visits and the planned efficacy analysis after all enrolled subjects have completed W12 are depicted in [Figure 3.1](#).

Figure 3.1: Study Schematic

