5.2.8.5 Multiplicity

5.2.9 Safety Analyses

Safety endpoints are:

- AEs, compared between 4 groups receiving one SP-102 injection, two SP-102 injections, placebo followed by SP-102 repeat injection, or placebo only.
- Change from Baseline (D1) in laboratory parameters.
- Change from Baseline (D1) in vital signs.
- Change from Baseline (D1) in neurological examination.

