## 7.10 Exposure to Study Drug

The number of randomized subjects that received index injection, that received repeat injection, and that received any injection will be summarized by treatment group.

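### AE percents by treatment and before/after the repeat injection cover unequal time at risk, so equal AE rates can show as a difference of either sign

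*SAP*

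**What the plan says.** Safety of single and repeat SP-102 is a secondary objective (Protocol 2.2, SAP 3.2). On timing, Protocol 3.1 says "The repeat injection may be administered between Weeks (W) 4 and 20", with follow-up for 24 weeks from the index injection.

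SAP 7.13.1 defines AE incidence as "number and percent of subjects reporting the AE at least once during the study". Some tables add event counts, for example "TEAE by system organ class and preferred term, incidence and number of events". Summaries are by treatment for three periods: the entire period, "Occurring after the randomization injection, but prior to a second injection (of SP-102", and after the second injection. On attribution, "AEs starting while on Placebo but before the repeat injection will be assigned to Placebo", and those starting at or after the repeat go to SP-102. SAP 7.10 describes exposure only as follows: "The number of randomized subjects that received index injection, that received repeat injection, and that received any injection will be summarized by treatment group".

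Other AE tables are also planned. SAP 7.13 has two arms over the first four weeks and four groups to Week 24. SAP 7.13.1 adds three presentations through Week 12: four groups, Exposed versus Not Exposed, and a placebo/SP-102 split within PBO/SP-102 subjects. Protocol 5.2.9 lists as a safety endpoint "AEs, compared between 4 groups receiving one SP-102 injection, two SP-102 injections, placebo followed by SP-102 repeat injection, or placebo only".

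The readable text gives no subject-time denominator, no exposure-adjusted rate, no fixed window after each injection, and no statement of which subjects form each percent's denominator. The table list in SAP 13 is blacked out, so table layouts cannot be checked.

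**The concern.** A crude percent is comparable between columns only if subjects had similar time in which to report an AE. In the whole-study by-treatment table, a placebo subject who repeats stops contributing placebo time and starts contributing SP-102 time. In the before/after tables, the timing of the repeat sets both window lengths. The percent after the second injection then reflects when the repeat was given as well as what it did. These are the tables a reader would use for repeat-injection safety, and without subject-time the reader can judge neither the size nor the sign of the distortion.

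**Working it through.** The readable documents give no AE rate and no expected repeat share, so there is no plan figure to reproduce. All rates, shares and hazard shapes below are assumptions. AE risk is set equal on the two treatments, so every gap is an artefact.

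**1. Windows, from the schedule.** For a repeat at week t, the time before it is t = 4 to 20 weeks (24 if there is no repeat) and the time after it is 24 - t = 4 to 20 weeks.

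**2. Whole-study table by treatment.** About 400 subjects randomised 1:1 gives 200 per arm. Let q be the share of placebo subjects who repeat, and risk(w) = 1 - exp(-λw). A 24-week risk of 30% gives λ = -ln(0.70)/24 = 0.01486 per week, hence risk(4) = 5.8% and risk(20) = 25.7%. The SAP states no denominators; I took 200 for placebo and 200 + 200q for SP-102:

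- Placebo % = (1 - q)·risk(24) + q·risk(t)
- SP-102 % = [risk(24) + q·risk(24 - t)] / (1 + q)

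For q = 50%, t = 4: placebo 0.5 × 30.0 + 0.5 × 5.8 = 17.9%; SP-102 (30.0 + 0.5 × 25.7)/1.5 = 28.6%.

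| Repeat week (q = 50%) | Placebo % | SP-102 % | Gap, points |
|---|---|---|---|
| 4 | 17.9 | 28.6 | +10.7 |
| 8 | 20.6 | 27.1 | +6.4 |
| 12 | 23.2 | 25.4 | +2.3 |
| 16 | 25.6 | 23.7 | -1.8 |
| 20 | 27.9 | 21.9 | -5.9 |

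Mean windows are equal at t = 24 - 24/(2 + q): Week 13.6, 14.4 and 15.1 for q = 30%, 50% and 70%. Over 24-week risks of 20%, 30% and 50%, those three values of q, and t from 4 to 20, the gap runs from +24.8 to -11.8 points.

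**3. Before the second injection** (same λ, repeats at Week 6).

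- Equal repeat shares: no gap.
- 30% of SP-102 and 60% of placebo subjects repeat: 23.6% v 17.1%, or +6.4 points from unrounded values.
- 60% of SP-102 and 40% of placebo subjects repeat: 17.1% v 21.4%, or -4.3 points.

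As a second parameter set, take 2% per week, 70% of placebo and 40% of SP-102 subjects repeating, and repeats either uniform over Weeks 4 to 20 or clustered soon after Week 4. Placebo is 21.5-26.1% and SP-102 28.6-31.3%. In this model the gap is proportional to the difference in repeat share. A 10-point difference in share gives (31.3 - 26.1)/3 = 1.7 to (28.6 - 21.5)/3 = 2.4 points.

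**4. Post-index v post-repeat, same subjects** (λ = 0.01486). Repeat at Week 4: 5.8% v 25.7%. At Week 12: 16.3% v 16.3%. At Week 20: 25.7% v 5.8%.

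**5. Twelve-week split within PBO/SP-102.** Windows are t and 12 - t. A Week 4 repeat gives 5.8% (placebo) v 11.2% (SP-102), Week 6 gives equality, and Week 10 gives 13.8% v 2.9%.

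**6. Hazard shape** (q = 50%, t = 6, 24-week risk 30%). Placebo v SP-102 is 19.3% v 27.8% at constant hazard, 27.7% v 29.5% if 80% of the hazard falls in the first 4 weeks after injection, and 30.0% v 30.0% if all of it does. As a simplification here and in step 2, SP-102 index subjects carry single-injection risk over all 24 weeks, so a second cluster after their own repeat is ignored.

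**7. Equal-window tables.** The two-arm 4-week table compares randomised groups before any planned repeat. The four-group and Exposed/Not Exposed tables have equal nominal windows, but membership depends on events after randomisation. A repeat needs continued participation, a qualifying pain score and no safety concern (Protocol 3.1). Subjects who leave before Week 4 can only fall in a no-repeat group; the plan's figures allow up to 400 - 332 = 68 without a completed Week 4. Exposed also carries the earlier placebo time of PBO/SP-102 subjects.

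**8. Does subject-time remove the artefact?** Simulation with equal hazard, 24-week risk 30%, q = 50%, repeats uniform over Weeks 4 to 12, and 200 per arm:

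- Crude: 20.4% v 27.3% (mean windows 16.0 v 21.3 weeks), ratio about 1.33.
- First events per 24 subject-weeks: 0.355 v 0.361, ratio about 1.02. Per 100 subject-weeks this is 0.355 × 100/24 = 1.48 v 0.361 × 100/24 = 1.50.
- Four-week window after each injection: 5.7% v 5.9%.

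**The case against.** The strongest reply has four parts.

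- **AEs may cluster.** Protocol 3.1 lists immediate and delayed procedural AEs and says long-term persistent ones are rarely seen. Under strong clustering the artefact nearly vanishes (step 6). This stands as a limit on size. It does not rescue the tables, since the plan cannot know the hazard shape in advance.
- **Inputs are chosen.** Neither document gives repeat shares or AE rates, and the SP-102 denominator in step 2 is inferred. This stands, so only a range is offered.
- **The plan already holds sound or equal-window tables, dated listings and event counts.** The 4-week randomised table is indeed sound. Listings and counts without subject-time do not make the before/after percents comparable.
- **No AE test is planned, so the percents are already descriptive.** That is so in the readable text, but Protocol 5.2.9 still frames the four groups as a comparison.

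A reader might infer more than the documents support:

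- *The bias always runs against SP-102.* It does if placebo subjects repeat earlier or more often, which is plausible if SP-102 works, because pain qualifies a subject from Week 4. Late repeats, or more repeats on SP-102, reverse it.
- *Only the 4-week table has equal windows.* The 12- and 24-week four-group and the 12-week Exposed/Not Exposed tables do too, nominally; their fault is grouping after randomisation.
- *Subjects choose the timing freely.* The repeat needs criteria, a pain score and investigator judgment.
- *Selection through AESIs is large.* Protocol 4.2.2 names three severe events, so the broader safety judgment is the more likely route.
- *Observation stops for everyone at Week 24.* Protocol 3.5.7.6 records AEs through Day 169, while 4.2.1 records them to 30 days after the last visit. On the second reading a Week 20 repeat has 28 + 30 = 58 days of AE recording, not 28.

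**Conclusion.** The point holds for the by-treatment, pre-repeat and post-repeat tables and for the 12-week split within PBO/SP-102: crude percents over windows of 4 to 24 weeks (t and 12 - t in the split) are not comparable. The direction is conditional. With equal risk, a 24-week risk of 30% and half of placebo subjects repeating, the whole-study gap is +10.7 to -5.9 points under constant hazard; over all values tried it is +24.8 to -11.8. It is near zero if AEs cluster within 4 weeks of injection. Repeat share, repeat timing, hazard shape and the SP-102 denominator are all assumptions.

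The primary safety contrast is not undermined, since the 4-week two-arm comparison is randomised and unaffected. Repeat-injection safety has no comparable estimate as planned, and the four-group and Exposed/Not Exposed tables do not support a causal comparison. The change should be made, but the trial does not depend on it.

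**What to change.** In SAP 7.13.1:

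1. State the denominator of every AE percent, including how a PBO/SP-102 subject counts in each treatment column.
2. For the by-treatment tables (including the 12-week PBO/SP-102 split) and the pre- and post-repeat tables, add subject-weeks at risk and TEAEs per 100 subject-weeks beside the percent. Time runs from index to the earlier of repeat or last contact, and from repeat to last contact; the 12-week split also stops at its cutoff.
3. Add a window of up to 28 days after each injection, cut at the repeat or last contact. Show it by randomised arm after the index, and within the same subjects after index and after repeat, for SP-102/SP-102 and PBO/SP-102 separately. A full 28 days is not guaranteed: the Week 4 visit may fall 3 days early, and some subjects leave. The window is needed beside the rates because, if AEs cluster, a rate averaged over a longer window is diluted.
4. Name the two-arm 4-week table as the main comparative safety table. Label the four-group and Exposed/Not Exposed percents descriptive.

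Reconcile Protocol 3.5.7.6 with 4.2.1 on when AE collection ends, since that sets the end of risk time.

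The cost is SAP wording and a few more tables from injection, contact and AE dates already collected, with no design change. The downside is that AEs after 28 days are covered only by the rate tables.
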